4.1 Main Study

Cohort 1 will enroll approximately 50 subjects aged 17 to 80 years to achieve at least 40 evaluable subjects.

Cohort 2 (children) will enroll approximately 25 subjects to achieve at least 20 evaluable subjects. Cohort 2 will enroll up to 6 subjects aged 2 to <6 years, at least 6 subjects 6 to <12 years, and at least 6 subjects aged 12 to <17 years.

4.2 PK Sub-study

Approximately 25 of the subjects in Cohort 1 will be enrolled in the PK sub-study to achieve at least 18 evaluable subjects for PK analysis.

Approximately 18 of the subjects from Cohort 2 will be enrolled in the PK sub-study to achieve at least 12 evaluable subjects for PK analysis. Up to 6 subjects will be analyzed for PK in each of the following age groups: 2 to <6 years, 6 to <12 years, and 12 to <17 years.

4.3 Eligibility Criteria

4.3.1 Inclusion Criteria

1. Subject is male or female between the ages of 2 and 80 years at Screening.
 - For Russian sites, only subjects 18 years of age and older, treated with commercially licensed immune globulin product will be enrolled.
 - For Cohort 1, all subjects will be aged ≥ 17 to 80 years.
 - For Cohort 2, subjects will be aged 2 to <17 years
2. Subject or parent(s)/legal guardian has given written informed consent/assent (as applicable). Pediatric subjects are defined as 2 to 17 years of age at study entry and will require assent forms as appropriate.
3. Subject or parent(s)/legal guardian agrees to comply with the requirements of the protocol.

4. Female subjects of childbearing potential must have a negative urine pregnancy test documented at the visit which they receive the first infusion of IMP and must agree to employ adequate birth control measures, as determined by their IRB/IEC, for the duration of the study.
5. The subject must have established one of the following three diagnoses (isolated PIDD of other types will be excluded):
 - Common variable immunodeficiency (CVID)
 - X-linked agammaglobulinemia (XLA)
 - Hyper-IgM syndrome and documented low IgG levels (<4.5 mg/mL [450 mg/dL]).
6. Subjects must have been treated with a stable dose of immune globulin administered intravenously (IGIV) or subcutaneously (IGSC), as defined below.
 - For IGIV, a stable dose is defined as administration of a dose of 200-800 mg/kg with no more than 25% change during at least 3 consecutive treatments at 21-day (± 4 days) or 28-day (± 4 days) dosing intervals.
 - For IGSC, a stable dose is defined as administration of a dose of 300-900 mg/kg/month IV (or Sub-cutaneous equivalent), regardless of dosing schedule, with no more than 25% change during at least 12 weeks.
7. Subjects who are receiving IGSC when they enter the study must have received at least one previous documented IGIV infusion without an associated serious adverse event.
8. Documented trough or steady state levels
 - Subjects who are receiving IGIV when they enter the study have at least 2 documented serum IgG trough levels of ≥ 5 mg/ mL measured in the prior 6 months. One of these can be the serum IgG level at Screening.
 - Subjects who are receiving IGSC have at least 2 documented serum IgG steady state levels of ≥ 5 mg/mL in the prior 24 weeks. One of these can be the serum IgG level at Screening.
9. Authorization to access personal health information.

4.3.2 Exclusion Criteria

1. Subject has secondary immunodeficiency or has been diagnosed with dysgammaglobulinemia or isolated IgG subclass deficiency.
2. Subject has ever had a history of severe anaphylactic or anaphylactoid reaction to immunoglobulins or other blood products.
3. Subject has a known history of immunoglobulin A (IgA) deficiency and known anti-IgA antibodies. (Note that subjects with IgA deficiency without known antibodies to IgA may be enrolled.)
4. Subject has had a thrombotic event, such as deep vein thrombosis, myocardial infarction, cerebrovascular accident, pulmonary embolism, at any time.
5. Subject has received blood products except IGIV, IGSC, or albumin within the previous 12 months.
6. Subject has participated in another study (except for IGIV, IGSC studies) within the previous 4 weeks.
7. Subject has had cancer in the past 5 years, except for basal cell or squamous cell cancers of the skin.
8. Subject has current or prior diagnosis of malignancies of lymphoid cells such as lymphocytic leukemia, non-Hodgkin's lymphoma, or immunodeficiency with thymoma.
9. Subject has known hypoalbuminemia (<3 gm/dL), protein-losing enteropathy, or nephrotic syndrome.
10. Subject has had a documented active infection within 7 days prior to Screening, or subject is on continuous prophylactic antibiotics. Subjects receiving a course of antibiotic treatment for a recent bacterial infection, which is controlled, can be enrolled into the study.
11. Subject is positive for human immunodeficiency virus (HIV)-1 or HIV-2.
12. Subject has a positive hepatitis C virus (HCV) or hepatitis B virus (HBV) nucleic acid test (NAT) performed either by qualitative or quantitative polymerase chain reaction (PCR) in the past 12 months.
13. Subject has levels of alanine aminotransferase (ALT) or aspartate aminotransferase (AST) >2.5 times the upper limit of normal (ULN).
14. Subject has serum creatinine >1.5 times the ULN or a severe chronic condition such as renal failure with proteinuria.
15. Subject has anemia with a hemoglobin level ≤ 8 g/dL.

16. Subject has severe neutropenia with neutrophil count ≤ 1000 per mm^3 or has lymphopenia with < 500 per mm^3 .
17. Subject is taking prednisone at a dose ≥ 0.15 mg/kg/day. (Topical steroids for skin conditions, steroid eye drops, chronic use of inhaled steroids for asthma, and intranasal steroids for rhinitis are allowed.) Exception: A brief course of systemic steroids above this threshold (i.e., a steroid burst) is allowed for treatment of a short-term condition such as an asthma exacerbation or poison ivy exposure.
18. Subject is receiving other immunosuppressive drugs or chemotherapy.
19. Subject has known atrial fibrillation requiring anticoagulant therapy; congestive heart failure (New York Heart Association Class III/IV); cardiomyopathy; or cardiac arrhythmia associated with thromboembolic events, unstable or advanced ischemic heart disease, or hyperviscosity.
20. Subject has known decreased Protein C and/or Protein S levels.
21. Subject is positive for antibodies to $\beta 2\text{GPI}$ and/or $\beta 2\text{GPI-DI}$ at Screening.
22. Female subject who is pregnant, breast-feeding, or planning a pregnancy during the course of the study.
23. A history of epilepsy or multiple episodes of migraine (defined as at least one episode within 6 months of enrolment) not completely controlled by medication, or any condition that is likely to interfere with evaluation of the IMP or satisfactory conduct of the study in the Investigator's opinion.

5 Efficacy, Safety, and Pharmacokinetic Endpoints

5.1 Efficacy Endpoints

5.1.1 Primary Endpoint

The rate of clinically documented SBIs, defined as:

- Bacterial pneumonia
- Bacteremia and septicemia
- Osteomyelitis / septic arthritis
- Bacterial meningitis
- Visceral abscess

5.1.2 Secondary Efficacy Endpoints

The following secondary efficacy endpoints will be assessed:

- Total serum IgG trough
- Number of episodes of fever ($\geq 100.4^{\circ}\text{F}$)
- Number of days out of work/school/kindergarten/day care or unable to perform normal daily activities due to infection
- Number of days of hospitalization due to infection
- Number of days of antibiotic use for infection prophylaxis and/or treatment
- Number and duration of infections other than acute serious bacterial infections

5.2 Safety Endpoints

Safety will be evaluated via the following assessments:

- All reported AEs
- Rate (per subject per infusion), severity, and relatedness of AEs
- Frequency of temporally associated AEs
- Infusional AEs
- Assessment of local tolerability to IMP infusions: Reactions at infusion site
- Adverse reactions/suspected adverse reactions
- Vital sign changes, including changes in systolic and diastolic blood pressure, heart rate, respiratory rate, and body temperature
- Changes from Screening in physical examination findings
- Changes from Baseline in laboratory parameters (blood chemistry, hematology, urinalysis, hemolysis, d-dimer, protein S, and protein C concentrations, titers of antibodies to $\beta 2\text{GPI}$ and $\beta 2\text{GPI-DI}$)
- Frequency of clinical signs of hemolysis and/or thrombosis within 72 hours after infusion of the IMP
- IGIV-associated hemolysis
- Changes from Screening in viral safety markers (HAV, HBV, HCV, HIV-1, HIV-2, and B19)
- Comparisons of safety variables during treatment with IMP and during the Waiting Period on commercial product will be made as described in Section 12.3.4.

5.3 Pharmacokinetic Endpoints

The PK profile will be analyzed for the following endpoints in subjects participating in the PK sub-study:

- Total IgG levels
- Area under the concentration-time curve over 1 dosing interval (AUC_{0-t})
- Area under the concentration-time curve extrapolated to zero concentration (AUC_{0-inf})
- Peak serum concentration (C_{max})
- Time to reach the peak serum concentration (T_{max})
- The volume of distribution at steady-state (V_{ss})
- Mean residence time (MRT)
- Total body clearance (CL)
- Terminal half-life ($t_{1/2}$)

6 Study Procedures/Evaluations

6.1 Medical History

During Screening, all subjects will provide a relevant medical history including surgeries during the past 2 years, serious bacterial infections documented in the last 5 years, medications taken in the last 4 weeks, and any adverse drug reactions (ADRs) in the past 6 months.

6.2 Subject Diary

To obtain some of the data for evaluation of secondary endpoints, each subject (or parent/guardian, as appropriate) will be asked to fill in a diary throughout the study. The diary will be given to the subject at the baseline visit (Infusion 1 IMP/CP), along with instructions on how to complete it. The subject will be asked to record the following information in the diary from the first study visit until the LTSV:

- Any episode of fever ($\geq 100.4^{\circ}\text{F}$) measured at home with a thermometer provided by the study staff
- The number of days out of work/school/kindergarten/day care or unable to perform normal activities due to the underlying PIDD
- Date and duration of any hospitalizations (in case hospitalization is not at the site/location where the subject is being treated in the study)
- Any antibiotic treatments or other medications and the number of separate occasions they are taken during the study period
- Any other changes in medical history

Each time a subject returns to the study site, the Subject Diary will be reviewed for completeness and accuracy. Any discrepancies, especially from the phone call documentation up to 72 hours will be corrected by the subject at each visit, as necessary. Staff will review concomitant medications, AEs, and other safety information contained on the Subject Diary prior to administering CP or IMP. In addition, any other safety information (for example, laboratory results from prior visits) will also be reviewed prior to administration of CP or IMP. The diary will be returned to the subject at each visit with instructions to complete the diary and return with the diary at the next visit. Thermometers will be replaced only if lost or not functioning.

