9.2 Concomitant Medications

The administration of concomitant medications, including topical steroids for skin conditions, steroid eye drops, chronic use of inhaled steroids for asthma, and intranasal steroids for rhinitis, is permitted during the study period in keeping with the standard of care for subjects with PIDD. A brief course of systemic steroids (i.e., a steroid burst) is allowed for treatment of a short-term condition such as an asthma exacerbation or poison ivy exposure. Any medications, including non-prescription medications, taken by the subject from 21 days (± 2 days) or 28 days (± 2 days) (depending on subjects' dosing interval) before baseline (Infusion 1) through the end of the study and the reason for use will be recorded and captured in the eCRF.

Hydration practices are allowed during the study. All fluids administered and the volumes used will be recorded and captured in the eCRF.

The use of pre-medication for pain relief and/or diphenhydramine prior to an IMP infusion is only permitted if the subject is using these pre-medications as part of routine IGIV or IGSC treatment.

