11.10. Subject Diary

Subject diary data will be used to derive the following secondary efficacy endpoints:

- Episodes of fever ($\geq 100.4^{\circ}\text{C}$)

- Number of days out of work/school/kindergarten/day care or unable to perform normal daily activities due to infection
- Number of days of hospitalization due to infection
- Number of days of antibiotic use for infection prophylaxis and/or treatment

The subject diary data will be tabulated and listed.

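### SAP 11.10 derives three infection-related secondary endpoints from diary items that, as listed in the protocol, cannot yield them; days lost is the firm problem because no other source is named

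*Protocol*

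**What the plan says.** Protocol 5.1.2 lists six secondary efficacy endpoints, repeated in Protocol 12.3.3 and SAP 10.2. Three matter here: days out of work or school or unable to perform normal activities because of infection, days in hospital because of infection, and "Number of days of antibiotic use for infection prophylaxis and/or treatment".

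SAP 11.10 states the data source: "Subject diary data will be used to derive the following secondary efficacy endpoints". Its list contains all three, including "Number of days out of work/school/kindergarten/day care or unable to perform normal daily activities due to infection". It gives no derivation rule.

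Protocol 6.2 describes what the diary collects:

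- Days lost: "The number of days out of work/school/kindergarten/day care or unable to perform normal activities due to the underlying PIDD".
- Hospital stays: the date and duration of any stay, explained as cover for admissions away from the study site. No reason for admission is listed.
- Antibiotics: "Any antibiotic treatments or other medications and the number of separate occasions they are taken during the study period".

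The same section introduces the diary with the words "To obtain some of the data for evaluation of secondary endpoints", so the protocol does not present it as the only source. Protocol 9.2 says that medications taken "through the end of the study and the reason for use will be recorded and captured in the eCRF".

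**The concern.** An endpoint can be derived only from data that carry its cause and its unit. For days lost, the diary asks about the underlying disease while the endpoint asks about infection. A subject with a primary immunodeficiency may lose days to that disease for reasons other than infection. For antibiotics, the diary asks for occasions while the endpoint is in days. For hospital stays, the diary has the duration but not the reason.

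If SAP 11.10 is followed literally, three of the six secondary endpoints would be reported under titles that the source items do not support. SAP 10.2 also shows the efficacy endpoints side by side for the commercial-product and IMP periods, so the mislabelling would appear in both columns of the study report.

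**Working it through.** No plan figure bears on this point, so there is nothing to reproduce. The check sets each endpoint against its diary item and then looks for another source in either document.

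| Endpoint (Protocol 5.1.2, SAP 11.10) | Diary item (Protocol 6.2) | Gap | Other source in the documents |
|---|---|---|---|
| Days lost due to infection | Number of days lost due to the underlying PIDD | Cause | None named |
| Hospital days due to infection | Date and duration of any stay | Cause missing | Inpatient admission makes an event an SAE (Protocol 10.1.4); the SAP records diagnosis, onset and resolution for every TEAE (SAP 11). Not linked to the endpoint |
| Days of antibiotic use for prophylaxis or treatment | Number of separate occasions medications are taken | Unit; no indication listed | Every medication and its reason for use go into the eCRF (Protocol 9.2). Start and stop dates are not mentioned, and SAP 11.6 summarizes medications only by class and generic name. Not linked to the endpoint |

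**Days lost.** The listed item is a number of days. Protocol 6.2 does not ask for the date of each day lost. Entries can therefore be matched to infection adverse events only if the diary form happens to hold dates, and the form is not in the documents.

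**Antibiotics.** The term for occasions is undefined, and its meaning decides the direction of the error. As an illustration on assumed figures that are not in the documents, take a subject with 2 courses a year, each lasting 7 to 14 days:

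- True antibiotic days: 2 × 7 = 14 to 2 × 14 = 28.
- Diary count if an occasion is a course: 2, an undercount.
- Diary count if an occasion is a dose taken 2 to 3 times daily: 14 × 2 = 28 to 28 × 3 = 84, an overcount.

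The same subject can thus be under- or overcounted, depending on how the item is read.

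**Hospital days.** The diary supplies the timing and length of the stay, and the SAE record supplies the diagnosis. Together they can give the endpoint, but SAP 11.10 names only the diary. Adverse-event onset and resolution dates bound the event rather than the admission, so both pieces are needed unless the SAE record holds admission and discharge dates.

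**The case against.** The strongest reply is that Protocol 6.2 is a summary list. The diary form and its instructions are not in the documents, the protocol calls the diary a source of only some of the data, and staff review it at each visit. For two of the three endpoints the missing information is probably held elsewhere: the reason for use of each medication in the eCRF, and the diagnosis for each admission in the SAE record. The endpoints are descriptive, no hypothesis is tested on them, and the same diary wording applies in both treatment periods.

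Much of this stands. It rules out saying that three endpoints will certainly be mis-measured, and it separates days lost from the other two. It does not answer the days-lost gap: a visit review checks an entry against the question asked and does not change that question. Nor does it supply the missing link in SAP 11.10, which names the diary and nothing else.

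A reader might also infer that the 13 or 17 infusion visits each add a day lost, inflating the endpoint by 13 to 17 days per subject-year. Nothing in the documents says that subjects record infusion visits as days lost to their disease, so that figure is not supported. Likewise, a reader might infer that antibiotic use will be undercounted. That holds only if an occasion is a course, which the documents do not say.

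**Conclusion.** The point holds as a mismatch between the stated source and the defined endpoints. The diary items as listed differ from the endpoints in cause (days lost), lack the cause (hospital days) or differ in unit (antibiotics), and neither document gives a rule to bridge the gap. Days lost is the firm problem. The antibiotic and hospital endpoints are repairable from records that the SAP does not cite for them.

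The size and direction of the error cannot be estimated from the documents. The consequence is limited to descriptive secondary results: the primary analysis of serious bacterial infections and its power are untouched. The conclusion assumes that the diary form follows the list in Protocol 6.2. If the form already asks about infection and records dates, only the wording of the two documents needs aligning.

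**What to change.** 1. **Diary, for remaining collection.** Reword the days-lost item so that it asks for days lost due to infection, with the date of each day.
2. **SAP 11.10, antibiotics.** Derive antibiotic days from eCRF concomitant-medication start and stop dates, for medications whose recorded indication is treatment or prophylaxis of infection. Prophylaxis must be included or the endpoint changes. Confirm first that start and stop dates are collected.
3. **SAP 11.10, hospital days.** Derive these from SAE/AE records with an infection diagnosis. Use admission and discharge dates where they are held, and otherwise the stay dates in the diary.
4. **Days-lost entries already collected.** Attribute a day to infection by overlap with infection adverse-event dates only where the diary holds dates. Otherwise report the entries as days lost due to PIDD and state the limitation.

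The cost is a small revision of the SAP and the diary. Early days-lost data may not be fully reclassifiable. Timing also matters: Protocol 1.4 dates FDA approval of Group 3 dosing to December 2016 and SAP V2.0 is dated September 2018, so the diary change may reach little of the follow-up. Items 2 to 4 then carry most of the benefit.

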6.3 Vital Signs

Vital signs, including systolic and diastolic blood pressure, heart rate, respiratory rate, and body temperature, will be recorded at Screening; at each infusion visit before, during, and after each infusion (IMP or CP), and at the LTSV.

At each infusion visit, vital signs will be measured at rest at the following time points:

- ≤30 minutes pre-infusion
- 10 minutes (±3 minutes) after the start of the infusion
- 10 minutes (±3 minutes) after each increase of the infusion rate
- 30 minutes post infusion (±5 minutes)
- 60 minutes post infusion (±15 minutes)

At the LTSV, vital signs will be recorded before administration of the subject's standard immunoglobulin treatment, but no post measurement is required.

6.4 Physical Examination

6.4.1 Organ Systems

A physical examination will be performed at each visit and will focus on organs or systems that are known to be the target of complications in PIDD: skin; head, eyes, ear, nose, and throat (HEENT), respiratory, cardiovascular, abdominal, breasts (optional), genitourinary (optional), rectal (optional), musculoskeletal, and neurologic.

6.4.2 Evaluation for Infection

When a subject is suspected of having an acute serious bacterial infection, the subject will be evaluated for the infection according to the *FDA Guidance for Industry: Safety, Efficacy, and Pharmacokinetic Studies to Support Marketing of Immune Globulin Intravenous (Human) as Replacement Therapy for Primary Humoral Immunodeficiency*, as outlined in Section 21.1.

All incidences of acute serious bacterial infection will be recorded in the electronic case report form (eCRF) together with the confirmatory tests for the diagnosis.

6.4.3 Height and Weight

Height will be recorded at Screening, and weight will be recorded at every visit.

6.4.4 Chest X-ray

All subjects will have a chest X-ray performed between the Screening visit and IMP Infusion 1, unless a chest X-ray has been performed within 6 months prior to the first study drug infusion (CP or IMP) and demonstrates a normal result or has shown no indication of active disease process, as determined by the PI/designee.

6.5 Pregnancy Testing

For female subjects of childbearing potential, a urine pregnancy test will be performed at every visit prior to infusion of IMP/CP.

6.6 Serum IgG Trough Levels

IgG trough levels will be determined from blood samples collected from all subjects at Screening, during the IMP treatment period prior to each infusion of IMP, and at the LTSV before the subject's standard IgG treatment. Subjects on CP Waiting Period need two IgG trough/steady state levels of ≥ 5 mg/ mL documented within 6 months prior to IMP Infusion 1.

6.7 Viral Safety Markers

Viral safety markers (HAV, HBV, HCV, HIV-1, HIV-2, and B19) will be tested as follows:

- Virology samples drawn at the following time points will be tested using NAT (preferably quantitative PCR, if available) and serology assays:
 - Blood samples will be obtained at Screening for determination of the subject's pre-exposure viral status and to exclude subjects with a positive test for any of the following viruses: HIV, HCV, or HBV in accordance with the exclusion criteria.
 - Prior to IMP dosing at IMP Infusion 1 when subject comes off CP Waiting Period
 - Prior to administration of the IMP at Week 12 (Infusion 5 for subjects on the 21-day cycle; Infusion 4 for subjects on the 28-day cycle)
 - Prior to administration of standard IgG at LTSV

- Retention samples for potential later testing will also be drawn prior to administration of the IMP/CP at the following visits:
 - Infusion 1 IMP/CP, Baseline for all subjects
 - LTSV
- Retention samples will be sent to the central laboratory and stored at -20°C or below for future viral testing if needed.
- All viral safety measurements will be performed by the central laboratory.

